6.3 Intent-to-Treat Analysis for the Primary Endpoint

An as randomized (formerly called "intent-to-treat") analysis, in which all available data on all randomized participants are included, will be used for the primary endpoint comparison between interventions.

6.4 Potential Effects of Missing Data on Secondary Endpoints

The possibility of missing data can have serious consequences for the interpretation of statistical analyses. This is particularly problematic if the probability of missing data is related to the intervention, the outcome, or both. There is a large statistical literature on the potential effects of missing data and also some proposed methods for analysis, although these methods often require assumptions that cannot be tested within the trial dataset itself. Some of the issues regarding the potential effects of missing data on the evaluation of secondary endpoints in this trial are briefly addressed below.

For measures recorded at 22-26 months corrected GA, some missing data due to loss-to-follow-up is to be expected, though minimal. Data for those subjects without 22-26 months data will be omitted from these analyses. Although these analyses will be conducted, it is important that the results be interpreted in light of the fact that they will only include a subgroup of the population ("completers"), and that the subgroup is based on outcomes such that the benefit of the original randomization may no longer hold. In the event that the analysis of the secondary endpoints at 22-26 months becomes an important issue for clinical decision-making, methods which directly model the outcomes and the withdrawal process may be considered.

7. Presentation and Format of Results

Examples of some of the tables described in the previous section are given in Appendix B. Additional tables and appropriate figures will be produced as needed. For general reporting, one decimal point for most efficacy and safety endpoints, p-values will be reported to two significant digits (following the ICJME conventions of x.xx for most, p>0.2, or p<0.001), and no rounding in any intermediate data or analysis steps will be used.

Data will be primarily managed in REDCap. SAS will be used for secondary data management and descriptive statistics. SAS datasets will be downloaded at least weekly from the study database for analysis. Graphics will be prepared using Stata v13 (or later) (Stata Corp, San Antonio TX, 2009) and the R programming package v 3.0 or later (The R Foundation for Statistical Computing, Vienna, Austria, 2011). Analyses will be implemented in SAS, Stata, or R as needed. These programs will be documented according to the Standard Operating Procedures of the Biostatistics and Epidemiology Consulting Center (BECC) and will be made available to sponsoring and regulatory agencies during study close out (See Manual of Procedures).

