Discharge Status	Clinical data: date of discharge or death, co-enrolled in other clinical trials, and respiratory status	Once a baby has been discharged, reached 44 weeks PMA or died, whichever occurs first
Record of Death	Clinical: date of death, primary cause of death; autopsy performed, if yes, provide narrative	If applicable
Neonatal Outcome Data	Clinical data: PDA (treated Y/N), IVH (grade), ROP stage > 1, BPD, and positive blood culture sepsis, and other complications	Once a baby has been discharged, reached 44 weeks PMA or died, whichever occurs first
Late Outcome Data	Clinical data: final date of discharge, transfer or death if after 44 weeks PMA; reason for continued hospitalization beyond 44 weeks PMA	If applicable, for infants who remain in hospital past 44 weeks PMA
Transfer Form	Clinical data: date of transfer, transfer to medical facility, foster care, etc.	If applicable, for infants who are transferred to an outside facility prior to reaching 36 weeks PMA
Follow-up Assessment at 22-26 months cGA	Clinical data: the incidence of ambulatory and non-ambulatory CP defined by Gross Motor Function Score (GMFCS); hydrocephalus shunt, microcephaly, or seizure disorder; presence of respiratory disease necessitating readmission before 22-26 months follow-up; all individual components of the composite outcome of Neurodevelopment Impairment NDI or death, including cognitive outcomes at follow-up at 1 SD cut-off on the Bayley Scale of Infant Development BSID III standardized scales, BSID III cognitive, language and motor scores at 2 SD cut-offs (<70) at follow-up.	Once a baby has had a 22-26 month cGA follow-up visit in clinic

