6.1. Statistical Plan

6.1.1. Sample Size Determination

Sample size is based on a possible reduction in risk of neonatal mortality/BDP in infants at 36 weeks PMA receiving the SI intervention compared to those who receive the standard PEEP/CPAP. The significance level was set at $\alpha=0.038$ (due to the interim analyses), and power at 80%. Based on information from the recent multi-center NICHD SUPPORT trial² and the COIN trial,²⁰ we estimate that the baseline rate of neonatal mortality/BDP in the standard or care (control) arm by 36 weeks is 65%.

In order to detect an absolute risk reduction of 12.5%, 263 subjects per treatment arm are required. We anticipate virtually no loss to follow-up for the primary endpoint as infants will likely still be hospitalized because of their condition, will be under constant and continuing medical care. We have inflated the estimate by 1.12 to allow for twins and multiples to be randomized together. With this inflation in mind, the target sample size for this study is 300 subjects per arm.

For the secondary outcomes available in all subjects, with 263 subjects per arm (ignoring the twin correction factor), there will be 80% power to detect a difference of 0.24 standard deviation units in continuous outcomes, and a hazard ratio of 0.77 in survival outcomes under a proportional hazards assumption. Some secondary outcomes will not be available due to death of the infant, or loss to follow-up after discharge from the NICU. Overestimating these rates at 50%, we assume 130 subjects per arm will be available for the longer term secondary outcomes. With this sample size we will still have sufficient power to detect a clinically meaningful difference of at least 17% in event rates (or odds ratio of at least 2.0).

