- 25. Duration of respiratory support (ventilation, CPAP, supplemental oxygen) in days (SA9)

22-26 Months corrected gestational age:

- 26. Neurodevelopmental outcomes (SA14)
- 27. Respiratory outcomes (SA14)

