6.2 Other Missing Data Considerations

In addition to data that is naturally missing from participants who withdraw from study, it is expected that there may be occasional missing values for other subjects. All attempts will be made to keep missing data to a minimum. Extensive procedures to minimize missing data during the data collection and entry process will be put in place, following standard operating procedures at the DCC. These procedures will be described further in the Manual of Procedures. In addition, since the infants are still hospitalized at 36 weeks PMA as part of routine clinical care, it has been our experience that this type of missing data is minimal. The number of subjects included with each individual analysis will be given with the results. In general, missing data will not be directly imputed in any way.

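### The only committed analysis at 22–26 months is complete-case; read with the rest of the plan it leaves out deaths as well as losses, and no death-or-impairment analysis is specified

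*SAP*

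**What the plan says.** SAP section 6.4 gives the rule for the 22–26 month measures: "Data for those subjects without 22-26 months data will be omitted from these analyses". The only cause of missing data it names there is loss to follow-up: "some missing data due to loss-to-follow-up is to be expected, though minimal". It then warns that "the subgroup is based on outcomes such that the benefit of the original randomization may no longer hold". If these endpoints become important for clinical decisions, "methods which directly model the outcomes and the withdrawal process may be considered". SAP section 6.2 adds: "In general, missing data will not be directly imputed in any way".

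The Protocol Summary and SAP section 2.1 both restrict these outcomes to survivors. Protocol section 6.1.1 is explicit about deaths: "Some secondary outcomes will not be available due to death of the infant, or loss to follow-up after discharge from the NICU". It overestimates the combined rate at 50%, leaving 130 infants per arm.

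The follow-up row of the data table in Protocol section 5 collects "all individual components of the composite outcome of Neurodevelopment Impairment NDI or death". SAP section 2.3.2 lists two endpoints at this visit, item 26 (neurodevelopmental) and item 27 (respiratory). It gives no composite, no definition of NDI and no rule for infants who have died.

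**The concern.** The protocol's Introduction expects SI, by reducing ventilation, to affect mortality as well as BPD, and death is half of the primary endpoint (SAP section 2.3.1). Survival to follow-up is therefore a post-randomisation event that treatment may change. If SI keeps alive some infants who would otherwise have died, and those infants are impaired more often than the rest, the SI survivors include a high-risk group with no counterpart in the control arm. The survivor comparison can then move against SI even though no infant was made worse. If SI raises mortality, the same mechanism can make it look protective.

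The warning in SAP section 6.4 describes this problem but changes no estimate. The alternative methods are optional, unspecified, and tied to a trigger that is not defined. SAP section 5 schedules the 22–26 month analysis separately, after the 36-week analysis, so a method left open now could be chosen with the primary result known.

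**Working it through.** **1. Do deaths fall under the omission rule?** SAP 6.4 does not mention death. Three other places settle the reading: the survivor restriction in the Protocol Summary, the same restriction in SAP 2.1, and Protocol 6.1.1, which names death first among the reasons for unavailability. Nothing in either document says how a death is counted at 22–26 months. That deaths are left out is a firm inference, not a stated rule.

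**2. The plan's own figure.** Protocol 6.1.1 says 130 per arm suffices for a 17-point difference, or an odds ratio of 2.0. The base rate and alpha for this statement are not given. Assume a 50% base rate, 33% in the other arm and two-sided alpha 0.05:

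- Mean rate = 0.415; pooled term √(2 × 0.415 × 0.585) = 0.697; unpooled term √(0.50 × 0.50 + 0.33 × 0.67) = 0.686.
- z = (0.17 × √130 − 1.96 × 0.697) / 0.686 = 0.83, so power = 0.798.
- Odds ratio = 1 / (0.33/0.67) = 2.03.

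Over base rates from 50% to 65%, power is 0.786 to 0.798 and the odds ratio 1.99 to 2.03. The figure reproduces at alpha 0.05. At alpha 0.038 power would be 0.751 to 0.763. The problem is not one of arithmetic.

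**3. Size of the distortion.** The documents give no mortality, impairment or loss rates, so every input here is an assumption. Suppose SI saves some infants and costs no lives, has no effect on impairment in infants who would survive in either arm, and no survivor is lost. Let dC and dS be mortality in control and SI, g = dC − dS, q0 the NDI rate in infants who survive either way, and q1 the NDI rate in the extra survivors.

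- Survivors-only difference (SI − control) = g(q1 − q0) / (1 − dS)
- Death-or-NDI difference (SI − control) = −g(1 − q1)

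One case: dC = 20%, dS = 15%, q0 = 40%, q1 = 80%.

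- NDI in survivors: control 40.0%; SI (0.80 × 0.40 + 0.05 × 0.80) / 0.85 = 42.4%. SI looks 2.4 points worse.
- Death or NDI: control 0.20 + 0.80 × 0.40 = 52.0%; SI 0.15 + 0.36 = 51.0%. SI is 1.0 point better.

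Range with g = 5 points, for mortality pairs 20/15, 25/20 and 30/25%:

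| q0, q1 | Survivors-only difference | Death-or-NDI difference |
|---|---|---|
| 40%, 60% | +1.2 to +1.3 | −2.0 |
| 40%, 80% | +2.4 to +2.7 | −1.0 |
| 30%, 70% | +2.4 to +2.7 | −1.5 |
| 40%, 100% | +3.5 to +4.0 | 0 |

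The more extreme pair q0 = 30%, q1 = 100% would give at most 0.05 × 0.70 / 0.75 = +4.7 in survivors and 0 for the composite.

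If SI instead raises mortality from 20% to 25%, with q0 = 40% and q1 from 60% to 100%, the survivors-only difference is −1.25 to −3.75 and the composite difference +2.0 to 0.

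**4. Precision.** A composite keeps deaths as events, so fewer infants are lost. The detectable difference at 80% power (base rate 50%, two-sided alpha 0.05, clustering of multiples ignored) is 17.1 points with 130 per arm, 13.9 with 200, 12.1 with 263 and 11.4 with 300. Where the composite falls depends on loss among survivors.

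**The case against.** The survivor population is declared in both documents, so it is a chosen estimand and not an accident of missing-data handling. Mortality is not ignored: SAP 2.3.2 analyses death by 36 weeks (item 18), death in hospital (item 21), and survival to discharge without major morbidity (item 22). Withdrawal at 22–26 months is compared between arms (SAP 4.3), and the randomisation characteristics of infants without complete follow-up are examined (SAP 6.1). The illustrated shifts are also small. At 130 per arm the standard error of a 40.0% versus 42.4% comparison is √((0.40 × 0.60 + 0.424 × 0.576) / 130) = 6.1 points, against a shift of 2.4.

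All of this stands. It limits the point to the direction and meaning of the estimate, since a shift of this size would rarely produce significance by itself. It does not remove the point. Separate mortality results and withdrawal comparisons help a reader to be cautious, but they do not supply a comparison that randomisation protects.

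Four stronger readings are tempting and are not supported:

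- *That the SAP abandoned a planned endpoint.* The composite appears by name only in the data table. The protocol's specific aim (2.2, item n) speaks of neurodevelopmental and respiratory outcome, and the SAP repeats that aim.
- *That SAP 6.4 expressly excludes deaths.* It does not; the exclusion is inferred. An infant who died has a known value on a death-or-NDI composite, so the omission rule would not remove that infant if the composite were analysed.
- *That this is the trial's main long-term safety result.* SAP 2.3.3 lists no safety endpoint at 22–26 months; neurodevelopment is listed under secondary efficacy.
- *That minimal loss in the SAP contradicts 50% in the protocol.* The protocol figure includes deaths and is a deliberate overestimate; the SAP figure concerns loss to follow-up alone.

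**Conclusion.** The point holds as a disclosed but unresolved weakness in a secondary analysis. The committed rule compares survivors who return, a group that treatment may shape, and the plan contains no analysis at 22–26 months that includes all randomised infants. Under a 5-point mortality benefit, the survivors-only difference could run from about +1 to +4 points while the composite difference runs from −2 to 0; the signs reverse if SI raises mortality.

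These figures rest wholly on assumed rates and on the extra survivors being impaired more often than the others, for which the documents give no evidence. If mortality does not differ between arms, the bias from deaths is likely to be small. Nor does the composite guarantee a benefit: in the range above it falls to zero. The primary analysis at 36 weeks is unaffected. This is a cheap improvement, best made before the 36-week results are known.

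**What to change.** Amend the SAP by the route in its section 8:

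1. Reconcile the follow-up row of the table in Protocol section 5 with items 26 and 27 of SAP 2.3.2.
2. Define NDI: state how the components combine and which Bayley cut-off applies. The protocol table gives both a 1 SD and a 2 SD (<70) cut-off and no combining rule.
3. Prespecify death or NDI by 22–26 months in all randomised infants, with deaths as events, using the GEE logistic model already planned in SAP 5.4.2.
4. Add a sensitivity analysis for survivors lost to follow-up, for example multiple imputation from neonatal data, written as an explicit exception to SAP 6.2. Its assumptions cannot be tested in the trial data and should be stated.
5. Keep the survivor-only neurodevelopmental and respiratory results, labelled as conditional on survival.

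The cost is drafting, agreement on an NDI definition and some imputation work. Deaths and the NDI components are already collected. The downside is that the composite weights death and impairment equally, so the two components must be reported separately beside it.

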8. REVISIONS TO THE DAMP

An attempt has been made to anticipate possible data problems and to pre-specify handling conventions. However, it is recognized that this DAMP may not have covered all possible issues related to data analysis and reporting. Blinded data reviews will be performed, and data problems found through such reviews will be handled according to the principles outlined in this DAMP and will be properly documented. Data problems found during final analysis will be handled in the same manner and will be clearly noted in study reports. Changes to these procedures that occur during the course of this study, will be incorporated as amendments to the DAMP and included in the protocol, if appropriate.

9. APPENDIX A: SCHEDULE OF STUDY REPORTING

Type of Report	Prepared By:	Provided To:	Frequency:
Serious Adverse Events (SAEs)	Sites, DCC	SC ¹ , DSMC, IRBs	Immediately
Patient Recruitment/Targets Data Quality, Timeliness	CDM ² , DCC CDM	SC SC, DSMC	weekly weekly quarterly 3-4 mos
Demographics (combined) Interim analysis:	Biostat ³ Biostat	SC, DSMC DSMC	quarterly 3-4 mos After 100, 200, 400 subjects complete 36 weeks PMA
Final analysis: Safety and Efficacy	Biostat	DSMC	100% accrual, follow-up after randomization until 36 weeks PMA.

SC denotes the SAIL Steering Committee, consisting of all site Investigators, the Data Coordinating Center (DCC), and NICHD representatives.
 CDM denotes clinical data management staff in the DCC.
 Biostat denotes staff biostatistician under the direction of the faculty biostatisticians in the

DCC.

10. APPENDIX B: DRAFT STUDY REPORT TABLES

The following are examples of some of the tables that may be included in final report for this clinical trial. Selected tables may also be used for reporting the results of the interim analyses. Although the exact content and format may change, an attempt has been made to summarize the most important population, safety, and efficacy data.

Table 1. Summary of Baseline Demographic Characteristics by Intervention Group

		A		В	T	otal	p-value
Number of Subjects	~n		~n		~n		
Clinical Site							
University of Pennsylvania	n	(%)	n	(%)	n	(%)	n/a
University of Melbourne	n	(%)	n	(%)	n	(%)	
etc.	n	(%)	n	(%)	n	(%)	
Consenting Procedure Used							
Antenatal	n	(%)	n	(%)	n	(%)	0.xx
Deferred	n	(%)	n	(%)	n	(%)	
Sex							
Male	n	(%)	n	(%)	n	(%)	0.xx
Female	n	(%)	n	(%)	n	(%)	
Race							
White/Caucasian	n	(%)	n	(%)	n	(%)	
Black/African-American	n	(%)	n	(%)	n	(%)	
etc.	n	(%)	n	(%)	n	(%)	
Gestational Age							
Median	X	X.X	X	X.X	Х	X.X	0.xx
Range	XX	to xx	XX	to xx	XX	to xx	
Maternal Age							
Median	X	X.X	X	X.X	Х	X.X	0.xx
Range	XX	to xx	XX	to xx	XX	to xx	
Maternal Gravidity							
Median	X	X.X	X	X.X	Х	X.X	0.xx
Range	XX	to xx	XX	to xx	XX	to xx	

Table 2. Summary of Baseline Clinical Characteristics by Intervention Group

		A		В	To	otal	p-value
Number of Subjects		~n		~n		~n	
Exposure to Antenatal Steroids							
No	n	(%)	n	(%)	n	(%)	0.xx
Yes	n	(%)	n	(%)	n	(%)	
Type of Antenatal Steroids (only in subset with exposure)							
	n	(%)	n	(%)	n	(%)	0.xx
	n	(%)	n	(%)	n	(%)	
Exposure to Medications to Prolong Pregnancy							
No	n	(%)	n	(%)	n	(%)	0.xx
Yes	n	(%)	n	(%)	n	(%)	
Placental Abruption							
No	n	(%)	n	(%)	n	(%)	0.xx
Yes	n	(%)	n	(%)	n	(%)	
Chorioamnionitis							
No	n	(%)	n	(%)	n	(%)	0.xx
Yes	n	(%)	n	(%)	n	(%)	
Membranes Rupture ≥ 24 hours before Delivery							
No	n	(%)	n	(%)	n	(%)	0.xx
Yes	n	(%)	n	(%)	n	(%)	
Mode of Delivery							
Vaginal	n	(%)	n	(%)	n	(%)	0.xx
C-Section	n	(%)	n	(%)	n	(%)	
Route of Intervention Administration							
Facemask	n	(%)	n	(%)	n	(%)	0.xx
Nasopharyngeal Tube	n	(%)	n	(%)	n	(%)	
		• /		. ,		. /	

Table 3: Screening and Eligibility

	Total
Total Infants Screened	~n
Eligible	n (%)
Ineligible	n (%)
Reasons for exclusion / ineligible:	
Baby was active, crying, HR>100bpm	n (%)
Considered non-viable	n (%)
Major anomaly (ies)	n (%)
Mother unable to consent	n = (%)
Parent refused consent	n (%)
Total Randomized	~n
Completed Study	n (%)
Completed 36 week PMA assessment	n = (%)
Completed first month of life	n (%)
Completed 48 hours post delivery	n (%)

Table 4: Subject Accounting by Intervention Arm

	A	В	Total
Total Randomized	~n	~n	~n
Completed Study	n (%)	n (%)	n (%)
Still on Study	n (%)	n (%)	n (%)
Discontinued Study:	n (%)	n (%)	n (%)
Violation of protocol	n (%)	n (%)	n (%)
Withdrawal of consent	n (%)	n (%)	n (%)
Adverse event	n (%)	n (%)	n (%)
Other	n (%)	n (%)	n (%)

Flow of Subjects Through Study Phases

[figure not shown]

Figure 1. Flow of Subjects Through Study Phases

Table 5. Cumulative Serious Adverse Events by Intervention Arm

		A	-	В	To	tal	p-value
Number of Subjects	~n		~n		~n		
Within the first 48 hours post delivery Death Oxygen Requirement (Fi02 ≥ 40% for 2 hours or more)	n n	(%) (%)	n n	(%) (%)	n n	(%) (%)	0.xx 0.xx
Within first 10 days of life: Pneumothorax Pulmonary Interstitial Eemphysema Pneumopericardium	n n n	(%) (%) (%)	n n n	(%) (%) (%)	n n n	(%) (%) (%)	0.xx 0.xx 0.xx
Grade 3 or 4 IVH Within first month of life: BPD	n n	(%) (%)	n n	(%)	n n	(%)	0.xx 0.xx
Other: XXX	n	(%)	n	(%)	n	(%)	0.xx

Table 6. Assessment of SI Intervention

	Total
Number of SI maneuvers performed	
1	%
2	0/0
2 SIs performed by Clinical Site	
University of Pennsylvania	%
University of Melbourne	%
etc.	%
Post SI intervention Respiratory Mode	
CPAP	%
PPV	%

NB: Percentages only in SI arm to maintain blinding until study completion.

Table 7. Primary Endpoint: Death or BPD at 36 weeks PMA

	A	В	Total	
Number of Subjects Randomized	~n	~n	~n	
Death/BPD Rate (p=0.xx) Death BPD	n (%) n (%) n (%)	\ /	n (%) n (%) n (%)	

11. APPENDIX C: STANDARD MONITORING REPORTS

The following are examples of the standard reports on patient recruitment, data quality, and demographics that will be prepared for the regular full Steering Committee meetings. These reports will also be sent to the DSMC as noted in Appendix A. *For details, please refer to the MOP (under development).*

SAIL Accrual and Data Reports Summary Generated (MM/DD/YYYY)

Notation: Tables 5 - 12 use only data that has been entered and verified. It may not include all infants that have completed a given time period assessment.

List of Reports

- **Table 1: Number of Participants Randomized**
- Table 2: Participant Randomization and Withdrawal Report
- Figure 1: Overall SAIL Randomization Profile
- Figure 2: SAIL Randomization Profiles by Clinical Center
- **Table 3:** Number of Participants With Completed Data The Randomization column represents the delivery room phase. For follow-up assessments, this report is based on data verified in the database as of the date shown. Therefore, it may not include all patients who have data at the stated gestational age.
- Table 4: Completion Rates Among Active Study Participants by Clinical Center
- Table 5: Age Distribution Gestational and Maternal
- **Table 6: Race Distribution**
- **Table 7: Gender Distribution**
- **Table 8:** Missing Forms (Number of Missing Forms, by Type of Form)
- Table 9: Timely Entry and Verification (Mean Number of Days from Date of Birth/Randomization to First Entry in Database)
- Table 10: Missing Values (Missing Fields Per Completed Forms, by Type of Form)
- Table 11: Query Rates (Fields Queried Per Completed Forms, by Type of Form)
- **Table 12: Adverse Event Reporting**
